3.2 Primary Objective

To conduct a feasibility trial of StopApp to estimate recruitment and attrition rates of participants across three settings: GP surgeries, community settings and on-line; at baseline, intervention access, and two-month follow-up.

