3.3 Secondary Objectives

Secondary objectives of the feasibility trial are to estimate the:

- **3.3.1** acceptability of randomisation and the StopApp intervention for participants
- **3.3.2** acceptability of primary and secondary outcome measures and measures required for cost-effectiveness and cost utility analyses in a future trial
- **3.3.3** key costs which would be incurred in delivering the intervention and usual care, including a comparison of non-attendance at SSS (Did-not-attend or DNA rates) between each arm of the trial.
- **3.3.4** feasibility of accessing SSS and GP data (if recruited via GP) on attendance, quit dates set and four-week quits for trial participants
- **3.3.5** any differential recruitment and attrition rates across socio-economic groups and age and gender
- **3.3.6** rate of SSS attendance in the treatment and control groups to estimate the event rate of the primary outcome measure for a future trial and support future trial sample size calculations

4. Methodology

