4.3.1 GP surgery recruitment

The study is eligible for adoption to the NIHR portfolio and the process of application has begun. We will apply for joint primary care and public health portfolio status. The Clinical Research Network (CRN) are supporting recruitment via GP surgeries. GP practices in Warwickshire have been invited to participate and of those who are interested, we will select four for the feasibility trial (stratified by indices of Deprivation, to ensure we are reaching diverse groups). Patients listed as smokers on the practice records will be checked by practice staff to ensure they meet the inclusion criteria (see 4.4 below) of being aged 16 years or older and a smoker. To remove the chances of contamination, we will contact one smoker per household only. Where two or more smokers cohabit, the resident whose first name is alphabetically first will be selected for invitation to the study and the other resident(s) will receive the control intervention (a web-based pdf with stop smoking service information) after the study has ended. Note: the reason for non-selection will not be provided to the co-habiting smoker to avoid disclosing that the selected resident is a smoker or participating in the study.

Smokers (one smoker per household) will be sent an email and/or text or letter (dependent on GP and patient communications set up) from their GP inviting them to take part in the 'MyWay' study. This will inform them that the study will investigate the best ways of using the internet to help people to stop smoking. Where a GP practice's preferred method of contact with patients is via postal letter, Docmail services will be used to distribute letters as recommended by the CRN. For ethical reasons we will not attempt to recruit people aged less than 16 years as they would typically require parental consent to participate in research and parents may not be aware of their child's smoking status. The email/text/letter (see appendix M & N) will include brief information and a web link/QR code to the study website where further

information and the secure electronic consent process can be accessed (see section 4.9 Procedure below for further information).

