4.3.2 Recruitment from other community settings

Contact has been made with the county council leads for libraries, wellbeing hubs, all pharmacies and all children's centres in Warwickshire, and with the family information service and the registrar's office in order to provide information about the proposed study and gain in principle agreement to support recruitment. We have so far gained in principle support from four pharmacies, over 30 children's centres, all seven wellbeing hubs, the family information service and the registrar's office and will be acting on further suggestions from our PPI group for community recruitment locations (e.g. dentists). Following suggestions from our PPI group, we will also be including bus stop and bus based advertising to aid recruitment.

We will supply each participating community setting with posters to display in prominent locations advertising the 'MyWay' study with contact details of the research team and a community-setting specific QR code to gain immediate access to the study website for participants. We will train all staff in participating locations about the study to enable them to answer any basic queries and to promote it confidently. We will also combine staff promotion of the study via leaflets and a very brief verbal introduction with ad hoc research assistant presence for active promotion and recruitment on site. Where staff provide a leaflet, access to the study will be either through QR code/web link to project website or via contact with the research team. Where a research assistant recruits on site, physical copies of the participant information sheet will be available and immediate access provided to the study via tablet computers. People will have the option to gain access to the study but consider participation and return later to the website to provide informed consent.

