4.11 Estimated recruitment rate and proposed sample size

The primary objective of this study is to assess the feasibility of recruitment to a potential future definitive RCT and therefore formal power analysis is not appropriate. However, in order to determine the target sample size we have drawn on two sources. Teare et al. (2014) recommend that external pilot and feasibility studies with binary outcome measures (in this case attend vs. does not attend SSS) recruit at least 60 participants in each group (minimum N=120) and a maximum of 100 participants in each group (maximum N=200). In addition, our sample size calculations, based on similar definitive RCT data about recruiting smokers to trials via letters from their GPs, suggested that we would need to enrol 980 smokers to detect a 7% difference between control and intervention arms in a definitive trial. Based on this estimate, any trial would need to recruit 1.8 participants per day to achieve the required recruitment in 18 months. We plan to recruit for three months, and based on needing to recruit 1.8 participants per day, we need to reach a required sample size of **162** participants (54 per setting). With a sample size of 162, the recruitment rate of smokers for a full RCT will be estimable with a precision (95% CI width) of +/- 5%.

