4.12 Statistical analysis plan

Feasibility and acceptability of all measures will be assessed by level of completeness and by follow-up qualitative interviews with a sub-sample of participants (see detail above on nested qualitative study). We will calculate recruitment rate via GP surgeries as a percentage of those recruited from those smokers identified on participating GPs lists. We will calculate recruitment via community and online settings as the time taken and spend required to recruit 54 participants and/or the number recruited and spend over three months. We will

calculate the average recruitment rate per day across the three settings. We will provide percentage rates for attrition across each recruitment setting at each of baseline, intervention/control access, and two-month follow-up.

We will look at the observed difference between intervention and control groups for bookings and attendance at SSS and use this data to support estimates for the required sample size for a definitive trial. Clinical significance will also be used in these estimates and a comparison of the two will help to determine future trial feasibility. We will assess level of completeness of all measures and run missing value analysis to determine whether any missing data are missing at random or whether patterns of missing data may indicate a problem with measures.

We will report observed and self-reported bookings, attendances, quit rates set and four-week quits across the intervention and control groups, and the proportion of participants agreeing to allow access to SSS and GP data (where relevant) relating to smoking status and SSS attendance.

We will report on numbers of higher versus lower SES status participants recruited as well as age and gender, and assess using chi-squared analysis whether SES status, age or gender are associated with attrition at baseline, intervention/control access and two-month follow-up.

5. Ethical Considerations

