The main purpose of the proposed feasibility study is to determine whether the main trial can be done. This will largely be determined by whether one or more of the recruitment settings is able to produce the required sample size for a future main trial. Based on the information discussed above we estimate that we need to recruit an average of at least 1.8 participants per day to make a future trial feasible. We will also use data collected about SES, age and gender of those recruited and lost through attrition to understand the health equity of the trial methodology.

7. Research Governance

The nominated sponsor for this research is [name], Associate Pro Vice Chancellor of Research at Coventry University. [name] has confirmed he is prepared to take on sponsorship of the study on behalf of Coventry University. The university has an Information Protection Unit that provides support and information to staff in ensuring they are fully compliant with all Information Governance requirements.

We have a Study Steering Committee (SSC) in place that will operate independently of the research team to assess research governance issues. This includes an independent chair, [name] who is also the public health speciality lead for the West Midlands Clinical Research Network (CRN), [name], a statistician form the Clinical Trials Unit (CTU) at the University of Warwick, members of our PPI group, [name], the tobacco control lead from Public Health Warwickshire, and [name], the tobacco control lead from Public Health England (West Midlands). The SSC will meet at project outset and shortly before each progress report is due to assess progress, data management and research governance issues. All data accessed and retrieved from the SSSs systems will be dealt with on secure servers and stored on password protected files accessible only to members of the research team. We will only seek data for those participants who have provided their expressed consent for us to do so. The outcome measures of this project are routinely collected and recorded by the IT systems in the SSS. The owners of PharmOutcomes and Outcomes4health (Pinnacle Health Ltd) have worked with us to ensure StopApp sends the relevant referral data (only name and mobile telephone number) to the system and stores no data on StopApp itself (user information) that would contravene Information Governance requirements. Instead all data is sent via a secure server to the existing Pinnacle Health system.

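### Attrition is tested against SES, age and gender without regard to recruitment setting, so the result cannot show whether lower-SES smokers are lost within the setting(s) that a main trial would keep

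*Protocol*

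**What the plan says.** Section 3.2 sets out to "estimate recruitment and attrition rates of participants across three settings: GP surgeries, community settings and on-line". Objective 3.3.5 adds "any differential recruitment and attrition rates across socio-economic groups and age and gender".

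Section 4.12 serves these two aims separately. For setting it says: "We will provide percentage rates for attrition across each recruitment setting at each of baseline, intervention/control access, and two-month follow-up". For equity it will "assess using chi-squared analysis whether SES status, age or gender are associated with attrition at baseline, intervention/control access and two-month follow-up". Nothing crosses the two, and the equity sentence names neither stratification nor adjustment.

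Section 6 makes feasibility depend largely on "whether one or more of the recruitment settings is able to produce the required sample size for a future main trial", and says that SES, age and gender data will inform the health equity of the method. Section 4.9.2 states that each participant's ID will carry the type of setting, through a separate project page for each.

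**The concern.** The plan treats setting as a possible source of difference in attrition and allows that a main trial may use only some settings. The equity test nevertheless averages over all of them. Two situations could give the same crude table. In one, a route that happens to reach more lower-SES smokers loses more people of every kind. In the other, lower-SES smokers are lost more often than others recruited by the same route. The first points to the mix of settings, the second to the procedures within them. The reverse is also possible: a real gap inside every setting can shrink in the crude table if lower-SES smokers come mostly through the setting with the best retention. And if a setting is dropped, an association averaged over three need not describe those that remain.

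**Working it through.** **The plan's own figure.** Section 4.11: 980 / (18 × 30 days) = 1.81, taken as 1.8 per day; 1.8 × 90 = 162; 162 / 3 = 54 per setting. These reproduce, and nothing below changes them.

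**Inputs.** From the Protocol: 54 per setting. Assumed, because the Protocol gives no values: the lower-SES share and the attrition rate in each setting.

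**Case A: no SES effect within any setting.** Assume lower-SES shares of 50%, 75% and 25% (GP, community, online), that is 27, 40.5 and 13.5 people, 81 in all. Attrition is 30%, 45% and 20%.
- Lower SES: (27 × 0.30 + 40.5 × 0.45 + 13.5 × 0.20) / 81 = 29.025 / 81 = 35.8%.
- Higher SES: (27 × 0.30 + 13.5 × 0.45 + 40.5 × 0.20) / 81 = 22.275 / 81 = 27.5%.
- Crude gap 8.3 points; gap within each setting 0.
- Pooled rate 31.7%. Standard error under the null = √(0.317 × 0.683 × 2/81) = 0.0731. Noncentrality = (0.0833 / 0.0731)² = 1.30. The 5% chi-squared test rejects in 20.7% of studies; a Cochran-Mantel-Haenszel (CMH) test stratified by setting rejects in about 5%.

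**Case B: a true 12-point gap in every setting.** Same shares, with attrition centred on 30%, 20% and 45% (6 points either side).
- Lower SES: (27 × 0.36 + 40.5 × 0.26 + 13.5 × 0.51) / 81 = 27.135 / 81 = 33.5%.
- Higher SES: (27 × 0.24 + 13.5 × 0.14 + 40.5 × 0.39) / 81 = 24.165 / 81 = 29.8%.
- Crude gap 3.7 points. The crude test rejects in about 8% of studies, CMH in about 32%.

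**Range.** 20,000 simulated studies per row, 54 per setting, two-sided 5%. Shares and attrition are listed for the three settings in the same order.

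| Lower-SES share (%) | Attrition (%) | Within-setting gap | Crude rates (%) | Crude test | CMH |
|---|---|---|---|---|---|
| 40/60/50 | 30/50/40 | none | 41.3 v 38.7 | 6.5% | 5.0% |
| 35/65/50 | 25/55/40 | none | 43.0 v 37.0 | 12.2% | 4.6% |
| 30/70/50 | 20/60/40 | none | 45.3 v 34.7 | 28.1% | 4.7% |
| 20/80/50 | 20/60/40 | none | 48.0 v 32.0 | 55.4% | 4.7% |
| 50/50/50 | 20/60/40 | none | 40.0 v 40.0 | 5.0% | 4.9% |
| 30/70/50 | 40/40/40 | none | 40.0 v 40.0 | 5.0% | 5.0% |
| 40/60/50 | lower SES 60/40/50, higher 40/20/30 | 20 points | 48.7 v 31.3 | 62% | 74% |
| 30/70/50 | lower SES 70/30/50, higher 50/10/30 | 20 points | 44.7 v 35.3 | 22% | 73% |

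So the crude and within-setting answers part only when SES mix and attrition both vary by setting, and materially only when they vary a good deal.

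**Precision.**
- Crude difference in case A: 1.96 × √(0.358 × 0.642/81 + 0.275 × 0.725/81) = ±14.3 points.
- Mantel-Haenszel risk difference in case A: weights n₁n₀/54 are 13.5, 10.125 and 10.125, sum 33.75. Variance = (13.5 × 0.21 + 10.125 × 0.2475 + 10.125 × 0.16) / 33.75² = 0.00611, giving ±15.3 points.
- One setting alone, 27 v 27 at 50% v 30%: 1.96 × √(0.46/27) = ±25.6 points, with power of about 32%.

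**The case against.** A reader might infer that the settings differ by design in deprivation and in completion. The Protocol does not support that. The phrase "stratified by indices of Deprivation, to ensure we are reaching diverse groups" in section 4.3.1 concerns the choice of four GP practices; it widens the mix inside one setting and fixes no contrast between settings. Contact does differ: in the community a research assistant may be present, with "immediate access provided to the study via tablet computers", and section 4.10.1 gives GP recruits a reminder of their own. But the assistant's presence is ad hoc, and section 4.10.2 emails the two-month questionnaire to everyone. Assisted completion would also, if anything, suggest lower early attrition in the community, the opposite of case A. This stands: differences between settings are possible, not established.

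A reader might also call a crude gap that arises through setting spurious. For this objective it is not. If lower-SES smokers are lost because of the route that reaches them, that is a real feature of the trial method, and adjusting for setting would remove it. The crude comparison therefore has to stay.

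The absence of stratification is read from silence, and a separate analysis plan could add it. That tempers the point, but section 4.12 is itself headed as the statistical analysis plan, names the test and places setting in a separate summary.

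Finally, no decision turns on the test. The only numerical criterion in section 6 is 1.8 recruits per day, and equity data are there for understanding. That limits the weight of the point without removing it.

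**Conclusion.** The point holds as a limitation of a secondary analysis. The planned chi-squared tests answer objective 3.3.5 overall but cannot say whether lower-SES smokers, or particular age or gender groups, are lost within the setting(s) a main trial would keep. How much this matters depends on settings differing in both SES mix and attrition, on which the Protocol has no figures. Under assumed inputs with no within-setting effect, the crude test rejects in about 6.5% of studies for modest differences, about 21% in case A and up to 55% in the most extreme case tried. There is no distortion if only one of the two varies. Masking can also occur: 12 true points seen as 3.7, or 20 seen as about 9. No stated figure is wrong because of this.

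**What to change.** Keep the crude tables in section 4.12. For intervention/control access and two-month follow-up, add:
- attrition by SES, age and gender within each setting, as counts and percentages;
- for each of the three characteristics, a setting-stratified estimate with a 95% CI: a Mantel-Haenszel risk difference, or logistic regression with setting as a term.

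State that these are exploratory estimates to be read beside the crude comparison, not in place of it. Separate tests within a setting should be avoided, given about 32% power for 50% v 30%.

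The addition cannot cover people lost before baseline completion. SES, age and gender come from the baseline questionnaire (sections 4.9.2 and 4.10.1), while registration takes only name and email, so section 4.12 should limit it to the later stages.

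The cost is a few lines of analysis and slightly wider intervals (±15.3 rather than ±14.3 points in case A). Setting is already tied to each ID, no new data are needed, and N stays 162.

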5.1 Risks and benefits

Risks - Participating in the proposed research has limited risk associated with it for participants. Consenting to participate will require participants to complete questionnaire measures and to access either an online information leaflet or the StopApp intervention. They will be required to make a decision about whether or not to book and then attend a SSS appointment and may then choose to go to that appointment, set a quit date and attempt to stop smoking. Risks associated with these actions are in line with normal every day risk and we will provide all study participants with information about how to access support for anything related to their participation in the study. Some smokers may attempt to quit and fail and this may have some negative psychological impacts in the short-term. Participants will also need to provide consent for data held about them and their smoking status by their GP and SSS to be accessed during the study. All such data will be handled in accordance with the latest data protection legislation and anonymised for the purposes of data analysis and reporting.

Potential benefits - There is the potential that some smokers who participate may actually quit smoking which has benefits to them and society. In addition, each quit attempt a smoker makes means they are a step closer to quitting for good (West, 2013) and so there is an overall long-term net benefit to this outcome should it occur.

5.2 Ethical arrangements

Ethical approval will be obtained via the Health Research Authority (HRA), Warwickshire County Council (who commission the SSS) and Coventry University. No potential participants will be contacted until all ethical and R&D approvals are in place.

As outlined above, there are no major risks associated with participating in the research. Participating GP surgeries will receive funding via the CRN to send out recruitment communications to smokers on their patient lists. Participant Information

details and clear consent statements will be available on the eNgage study websites (for feasibility study and qualitative process evaluation) providing a full explanation of the research and what participation involves. Only those who actively opt in to the study and provide full informed consent to participate will able to participate. Participants in the feasibility RCT will be asked explicitly to consent to access to information about their smoking status and records via their GP and/or SSS (this is not mandatory for participation). Only where they have explicitly provided written consent for this will the research team gain access to this information. Participants will be made fully aware of their right to withdraw from the research up to the point of data analysis without needing to give a reason. They will be made aware of exactly how to go about this and all data provided by them will be withdrawn from the dataset and destroyed. Information about the confidentiality and anonymity of their data will be made absolutely clear to participants and we will tell people how their information will be treated and stored and what we will be doing with this. We will ensure that all use of data complies with the most recent data protection requirements and that information governance protocols are strictly adhered to. Participants will be given sources of information, advice and support in relation to issues that being involved may raise for them.

6. Stop/go criteria

The main purpose of the proposed feasibility study is to determine whether the main trial can be done. This will largely be determined by whether one or more of the recruitment settings is able to produce the required sample size for a future main trial. Based on the information discussed above we estimate that we need to recruit an average of at least 1.8 participants per day to make a future trial feasible. We will also use data collected about SES, age and gender of those recruited and lost through attrition to understand the health equity of the trial methodology.

7. Research Governance

The nominated sponsor for this research is [name], Associate Pro Vice Chancellor of Research at Coventry University. [name] has confirmed he is prepared to take on sponsorship of the study on behalf of Coventry University. The university has an Information Protection Unit that provides support and information to staff in ensuring they are fully compliant with all Information Governance requirements.

We have a Study Steering Committee (SSC) in place that will operate independently of the research team to assess research governance issues. This includes an independent chair, [name] who is also the public health speciality lead for the West Midlands Clinical Research Network (CRN), [name], a statistician form the Clinical Trials Unit (CTU) at the University of Warwick, members of our PPI group, [name], the tobacco control lead from Public Health Warwickshire, and [name], the tobacco control lead from Public Health England (West Midlands). The SSC will meet at project outset and shortly before each progress report is due to assess progress, data management and research governance issues. All data accessed and retrieved from the SSSs systems will be dealt with on secure servers and stored on password protected files accessible only to members of the research team. We will only seek data for those participants who have provided their expressed consent for us to do so. The outcome measures of this project are routinely collected and recorded by the IT systems in the SSS. The owners of PharmOutcomes and Outcomes4health (Pinnacle Health Ltd) have worked with us to ensure StopApp sends the relevant referral data (only name and mobile telephone number) to the system and stores no data on StopApp itself (user information) that would contravene Information Governance requirements. Instead all data is sent via a secure server to the existing Pinnacle Health system.

